Discontinued prior to Week 24	xxx (xx.x)	xxx (xx.x)	xxx (xx.x)	xxx (xx.x)	xxx (xx.x)
Data missing/out of window	xxx (xx.x)	xxx (xx.x)	xxx (xx.x)	xxx (xx.x)	xxx (xx.x)

PROGRAM\OUTPUT: T\_XXXXX.SAS\T\_XXXXXX.LST

DATE (TIME) : DDMMYY (HH:MM)

[1]: 95% CI is from exact binomial distribution.  
 Reference: Listing 16.2.6.

PROTOCOL: INCB 18424-258  
DRUG/INDICATION: Ruxolitinib/Myelofibrosis

(Page 1 of 1)  
VERSION: Final

Table 14.2.2.3

Summary of Proportion of Subjects with  $\geq 10\%$  Reduction from Baseline in Spleen Volume at Week 24  
by Final Titrated Dose Group  
(Population: ITT Subjects)

NOTE TO THE PROGRAMMER: this table will be programmed similarly to Table 14.2.2.2.

PROTOCOL: INCB 18424-258  
DRUG/INDICATION: Ruxolitinib/Myelofibrosis

(Page 1 of 2)  
VERSION: Final

Table 14.2.3.1

Summary of Total Symptom Score by Study Week and Final Titrated Dose Group  
(Population: ITT Subjects)

NOTE TO THE PROGRAMMER: this table will be programmed similarly to Table 14.2.2.1 but Study Weeks will be 0, 4, 8, 12, 16, 20, 24.

PROTOCOL: INCB 18424-258  
DRUG/INDICATION: Ruxolitinib/Myelofibrosis

(Page 1 of 1)  
VERSION: Final

Table 14.2.3.2

Summary of Proportion of Subjects with  $\geq 50\%$  Reduction from Baseline in Total Symptom Score  
by Study Week and Final Titrated Dose Group  
(Population: ITT Subjects)

NOTE TO THE PROGRAMMER: this table will be similarly program as Table 14.2.2.2 but will not derive/display reason of not achieving a response.

PROTOCOL: INCB 18424-258  
DRUG/INDICATION: Ruxolitinib/Myelofibrosis

(Page 1 of 1)  
VERSION: Final

A table that has been completely redacted with black boxes. Only the header row is partially visible, showing a single column with a redacted title.

NOTE TO THE PROGRAMMER: this table will be similarly program as Table 14.2.2.2 but will not derive/display reason of not achieving a response.

PROTOCOL: INCB 18424-258  
DRUG/INDICATION: Ruxolitinib/Myelofibrosis

(Page 1 of 2)  
VERSION: Final

Table 14.2.4.1

Summary of Spleen Palpation Length Data by Study Week and Final Titrated Dose Group  
(Population: ITT Subjects)

NOTE TO THE PROGRAMMER: this table will be programmed similarly to Table 14.2.2.1 but Study Weeks will be the nominal weeks where spleen length data are scheduled to be collected.

PROTOCOL: INCB 18424-258  
DRUG/INDICATION: Ruxolitinib/Myelofibrosis

(Page 1 of 1)  
VERSION: Final

Table 14.2.4.2

Summary of Proportion of Subjects with  $\geq 50\%$  Reduction from Baseline in Spleen Palpation Length  
by Study Week and Final Titrated Dose Group  
(Population: ITT Subjects)

NOTE TO THE PROGRAMMER: this table will be similarly program as Table 14.2.2.2 but will not derive/display reason of not achieving a response.

PROTOCOL: INCB 18424-258  
DRUG/INDICATION: Ruxolitinib/Myelofibrosis

(Page 1 of 1)  
VERSION: Final

Table 14.2.4.3

Summary of Proportion of Subjects with  $\geq 20\%$  Reduction from Baseline in Spleen Palpation Length  
by Study Week and Final Titrated Dose Group  
(Population: ITT Subjects)

NOTE TO THE PROGRAMMER: this table will be similarly program as Table 14.2.2.2 but will not derive/display reason of not achieving a response.

PROTOCOL: INCB 18424-258  
DRUG/INDICATION: Ruxolitinib/Myelofibrosis

(Page 1 of 1)  
VERSION: Final

Table 14.2.5.1

Summary of Patient Global Impression of Change Score by Study Week and Final Titrated Dose Group  
(Population: ITT Subjects)

NOTE TO THE PROGRAMMER: this table will be similarly program as Table 14.2.2.1 but no change and percent change will be derived.

PROTOCOL: INCB 18424-258  
DRUG/INDICATION: Ruxolitinib/Myelofibrosis

(Page 1 of 1)  
VERSION: Final

NOTE TO THE PROGRAMMER: this table will be similarly program as Table 14.2.2.1.

PROTOCOL: INCB 18424-258  
DRUG/INDICATION: Ruxolitinib/Myelofibrosis

(Page 1 of 1)  
VERSION: Final

NOTE TO THE PROGRAMMER: this table will be similarly program as Table 14.2.2.1.

PROTOCOL: INCB 18424-258  
 DRUG/INDICATION: Ruxolitinib/Myelofibrosis

(Page 1 of 3)  
 VERSION: Final

Table 14.3.1.1

Summary of Exposure and Duration of Exposure to Study Medication Through Week 24 by Final Titrate Dose Level  
 (Population: Safety Evaluable Subjects)

Variable	Ruxolitinib Final Titrated Dose (mg)				
	Total (N=xxx)	< 5 (N=xx)	>5 to 15 (N=xx)	>15 to 25 (N=xx)	>25 (N=xx)
Duration of Treatment (weeks) [1]					
n	xxx	xx	xx	xx	xx
Mean	xxxx.x	xxxx.x	xxxx.x	xxxx.x	xxxx.x
Std	xxxx.xx	xxxx.xx	xxxx.xx	xxxx.xx	xxxx.xx
Median	xxxx.x	xxxxx.x	xxxx.x	xxxx.x	xxxx.x
Min, Max	(xx.x, xx.x)	(xx.x, xx.x)	(xx.x, xx.x)	(xx.x, xx.x)	(xx.x, xx.x)
<=30 Days	xx (xx.x)	xx (xx.x)	xx (xx.x)	xx (xx.x)	xx (xx.x)
31-90 Days	xx (xx.x)	xx (xx.x)	xx (xx.x)	xx (xx.x)	xx (xx.x)
91-120 Days	xx (xx.x)	xx (xx.x)	xx (xx.x)	xx (xx.x)	xx (xx.x)
121-150 Days	xx (xx.x)	xx (xx.x)	xx (xx.x)	xx (xx.x)	xx (xx.x)
>150 Days	xx (xx.x)	xx (xx.x)	xx (xx.x)	xx (xx.x)	xx (xx.x)
Patient Year [2]	x.xx	x.xx	x.xx	x.xx	x.xx

PROGRAM\OUTPUT: T\_xxxx.SAS\T\_xxxx.LST

DATE (TIME): ddmmyy (hh:mm)

[1] Duration of treatment is calculated as (last dose date during the treatment period - first dose date +1)/7  
 disregard interruptions in between.

[2] Patient year is calculated based on duration of treatment.

[3] Average daily dose is calculated as total dose (mg) divided by duration of treatment expressed in days.

[4] Overall compliance is calculated as (total # of tablets consumed)/(total # of tablets expected to be consumed)\*100,  
 where total # of tablets expected to be consumed is based on prescribed doses (including interruption) from CRF  
 domain of EX.

Reference: Listing 16.2.7.1.1.

PROTOCOL: INCB 18424-258  
 DRUG/INDICATION: Ruxolitinib/Myelofibrosis

(Page 2 of 3)  
 VERSION: Final

Table 14.3.1.1

Summary of Exposure and Duration of Exposure to Study Medication Through Week 24 by Final Titrate Dose Level  
 (Population: Safety Evaluable Subjects)

Variable	Ruxolitinib Final Titrated Dose (mg)				
	Total (N=xxx)	< 5 (N=xx)	>5 to 15 (N=xx)	>15 to 25 (N=xx)	>25 (N=xx)
Average Daily Dose (mg) [3]					
n	xxx	xx	xx	xx	xx
Mean	xxxx.x	xxxx.x	xxxx.x	xxxx.x	xxxx.x
Std	xxxx.xx	xxxx.xx	xxxx.xx	xxxx.xx	xxxx.xx
Median	xxxx.x	xxxxx.x	xxxx.x	xxxx.x	xxxx.x
Min, Max	(xx.x, xx.x)	(xx.x, xx.x)	(xx.x, xx.x)	(xx.x, xx.x)	(xx.x, xx.x)
Last 7 Days Average Daily Dose (mg)					
n	xxx	xx	xx	xx	xx
Mean	xxxx.x	xxxx.x	xxxx.x	xxxx.x	xxxx.x
Std	xxxx.xx	xxxx.xx	xxxx.xx	xxxx.xx	xxxx.xx
Median	xxxx.x	xxxxx.x	xxxx.x	xxxx.x	xxxx.x
Min, Max	(xx.x, xx.x)	(xx.x, xx.x)	(xx.x, xx.x)	(xx.x, xx.x)	(xx.x, xx.x)

PROGRAM\OUTPUT: T\_xxxx.SAS\T\_xxxx.LST

DATE (TIME): ddmmyy (hh:mm)

[1] Duration of treatment is calculated as (last dose date during the treatment period - first dose date +1)/7  
 disregard interruptions in between.

[2] Patient year is calculated based on duration of treatment.

[3] Average daily dose is calculated as total dose (mg) divided by duration of treatment expressed in days.

[4] Overall compliance is calculated as (total # of tablets consumed)/(total # of tablets expected to be consumed)\*100,  
 where total # of tablets expected to be consumed is based on prescribed doses (including interruption) from CRF  
 domain of EX.

Reference: Listing 16.2.7.1.1.

PROTOCOL: INCB 18424-258  
 DRUG/INDICATION: Ruxolitinib/Myelofibrosis

(Page 3 of 3)  
 VERSION: Final

Table 14.3.1.1

Summary of Exposure and Duration of Exposure to Study Medication Through Week 24 by Final Titrate Dose Level  
 (Population: Safety Evaluable Subjects)

Variable	Ruxolitinib Final Titrated Dose (mg)				
	Total (N=xxx)	< 5 (N=xx)	>5 to 15 (N=xx)	>15 to 25 (N=xx)	>25 (N=xx)
Overall Compliance (%) [4]					
<=50	xx (xx.x)	xx (xx.x)	xx (xx.x)	xx (xx.x)	xx (xx.x)
>51-80	xx (xx.x)	xx (xx.x)	xx (xx.x)	xx (xx.x)	xx (xx.x)
>80	xx (xx.x)	xx (xx.x)	xx (xx.x)	xx (xx.x)	xx (xx.x)

PROGRAM\OUTPUT: T\_xxxx.SAS\T\_xxxx.LST

DATE(TIME): ddmmyy(hh:mm)

[1] Duration of treatment is calculated as (last dose date during the treatment period - first dose date +1)/7  
 disregard interruptions in between.

[2] Patient year is calculated based on duration of treatment.

[3] Average daily dose is calculated as total dose (mg) divided by duration of treatment expressed in days.

[4] Overall compliance is calculated as (total # of tablets consumed)/(total # of tablets expected to be consumed)\*100,  
 where total # of tablets expected to be consumed is based on prescribed doses (including interruption) from CRF  
 domain of EX.

Reference: Listing 16.2.7.1.1.

PROTOCOL: INCB 18424-258  
DRUG/INDICATION: Ruxolitinib/Myelofibrosis

(Page 3 of 3)  
VERSION: Final

Table 14.3.1.2

Summary of Exposure and Duration of Exposure to Study Medication Through Week 4 by Final Titrate Dose Level  
(Population: Safety Evaluable Subjects)

NOTE TO THE PROGRAMMER: this table will be programmed similarly to Table 14.3.1.1 but present only average daily dose.

PROTOCOL: INCB 18424-258  
 DRUG/INDICATION: Ruxolitinib/Myelofibrosis

(Page 3 of 3)  
 VERSION: Final

Table 14.3.1.3

Summary of Average Daily Dose of Ruxolitinib by Study Week and Final Titrate Dose Level  
 (Population: Safety Evaluable Subjects)

Variable	Ruxolitinib Final Titrated Dose (mg)				
	Total (N=xxx)	< 5 (N=xx)	>5 to 15 (N=xx)	>15 to 25 (N=xx)	>25 (N=xx)
Average Daily Dose (mg) for Week 1					
n	xxx	xx	xx	xx	xx
Mean	xxxx.x	xxxx.x	xxxx.x	xxxx.x	xxxx.x
Std	xxxx.xx	xxxx.xx	xxxx.xx	xxxx.xx	xxxx.xx
Median	xxxx.x	xxxxx.x	xxxx.x	xxxx.x	xxxx.x
Min, Max	(xx.x, xx.x)	(xx.x, xx.x)	(xx.x, xx.x)	(xx.x, xx.x)	(xx.x, xx.x)
Average Daily Dose (mg) for Week 2					
. . . .					

PROGRAM\OUTPUT: T\_xxxx.SAS\T\_xxxx.LST

DATE (TIME) : ddmmyy (hh:mm)

Reference: Listing 16.2.7.1.1.

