4.1.5. Interim Analysis Data from Study INCB 18424-258

In Study INCB 18424-258, subjects with platelet counts of 50 to $100 \times 10^9/L$ were enrolled to begin administration of ruxolitinib at 5 mg BID, which is a dose that represents a conservatively low starting dose, that data from earlier studies suggested should have a limited impact on platelet count. Subjects could then titrate their dose to an appropriate dose that offers benefit (eg, symptomatic and/or spleen size improvements) with cautious monitoring to avoid levels of thrombocytopenia associated with higher risk of spontaneous hemorrhage. Ruxolitinib administration was interrupted for a platelet count below $25 \times 10^9/L$ or for Grade 2 or higher hemorrhage events.

The study is currently in the enrollment phase; however, an interim analysis was conducted based on a data cutoff when it was expected that at least 20 subjects would have completed 24 weeks of treatment. At the time of the interim analysis, a total of 50 subjects had enrolled in the study. Of the 50 subjects enrolled, 33 (66.0%) subjects completed the Week 24 visit,

8 (16.0%) discontinued prior to Week 24, and 9 (18.0%) subjects remained on study and had not yet completed their Week 24 visit.

Most subjects were titrated to a ruxolitinib dose of 10 mg BID or higher by Week 24 and 20.0% of subjects had a $\geq 35\%$ reduction in spleen volume at Week 24. This is consistent with the proportion of subjects in Study INCB 18424-351 who had a $\geq 35\%$ reduction in spleen volume at Week 24 who initiated treatment at a dose of 15 mg BID (21.8%), and substantially higher than that observed for placebo-treated subjects in Study INCB 18424-351 (1.7%). In addition, Mesa et al (2011) has shown that a spleen volume reduction of $\geq 10\%$ is associated with meaningful improvements in symptoms and other measures of patient-perceived benefit (Patient Global Impression of Change [PGIC] and Myelofibrosis Symptom Assessment Form [MFSAF v2.0]).

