8.6.1. Dose Increases

Dose increases are optional.

During the core treatment phase, doses of ruxolitinib may be increased in 5 mg qd increments up to a dose of 10 mg bid starting at the Week 4 visit and at subsequent study visits. Dose increases can occur no more frequently than every 4 weeks, and only if:

- Platelet count was always $\geq 40 \times 10^9/L$ since the last scheduled study visit
- Platelet count, if decreased since the last scheduled study visit, is decreased by no more than 20% of the platelet count at the last scheduled visit
- No dose decreases or holds for safety have occurred during the preceding 4-week interval
- $ANC > 1.0 \times 10^9/L$ since the last scheduled study visit.
- For subjects with prior \geq Grade 2 hemorrhage events, please see below under [Section 8.6.3.4](#), Restarting with Resolution of Hemorrhage Events

Doses may not exceed 10 mg bid except in subjects who continue to meet the above dose escalation criteria, and who have, in addition, a PGIC score of 3 (minimally improved) to 7 (very much worse) while receiving 10 mg bid. Such subjects may continue dose escalation to a maximum dose of 15 mg bid. Note that when a 5 mg qd increment is added, creating a regimen such as 5 mg/10 mg, the higher dose should be taken in the evening and the lower dose in the morning.

During the extended treatment phase, doses of ruxolitinib may be increased in 5 mg qd increments up to a dose of 25 mg bid if the subject meets the above dose escalation criteria, or per the investigator's discretion.

Doses may never exceed 25 mg bid.

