## 4. STUDY DESIGN

### 4.1. Overall Description

This is an open label study of 24 weeks duration of ruxolitinib in subjects with PMF, PPV-MF, and PET-MF. The study is comprised of 4 phases (see protocol Section 7.1, Overall Study Design):

**Screening:** up to 21 days.

**Baseline:** exactly 7 days.

**Treatment Phase:** 24 weeks. For subjects receiving benefit from treatment, further participation may continue up to the time of commercial availability of ruxolitinib.

**Follow-up Phase:** 30 to 37 days after the last dose of ruxolitinib is taken.

All subjects will begin dosing at 5 mg bid ruxolitinib. Doses should be taken morning and evening, approximately 12 hours apart, and without regard to food.

Doses of ruxolitinib may be increased in 5 mg qd increments up to 10 mg bid starting at the Week 4 visit and at subsequent study visits (no more than every 4 weeks) if subjects meet prespecified criteria (refer to protocol Section 8.6, Dose Adjustments).

Doses may not exceed 10 mg bid except in subjects who continue to meet the dose escalation criteria (see Protocol, Section 8.6, Dose Adjustments), and who have, in addition, a PGIC score of minimally worse, much worse, or very much worse while receiving 10 mg bid. Such subjects may continue dose escalation to a maximum dose of 15 mg bid.

Doses may never exceed 15 mg bid, and no dose increases may occur after Week 16.

Subjects will be required to decrease the dose for platelet count  $< 35 \times 10^9/L$ , and to hold administration for platelet count  $< 25 \times 10^9/L$ . Subjects will have the option to restart or re-escalate the dose with improving platelet count.

Subjects will be required to interrupt administration for any Grade 2 or higher hemorrhage events. Subjects will be able to restart ruxolitinib administration with resolution of Grade 2 events; restart after a second event requires review and discussion of pertinent data with the sponsor. Restarts of ruxolitinib will only be permitted in some cases of Grade 3 and 4 events, after review and discussion of pertinent data with the sponsor.

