### 5.3.2. Intent-to-Treat Population

All subjects who are enrolled and have taken at least 1 dose of study drug constitute the intent-to-treat (ITT) population. All efficacy analyses will be conducted using the ITT population. It is noted that the ITT population is effectively identical to the safety population for this study.

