### 5.9.3. Dosing Level and Compliance

#### 5.9.3.1. Final Titrated Dose Level

The analytic value of the last titrated dose level will be derived as the average of the total daily dose (excluding periods of dose interruption) during the time interval of Day 141 and Day 168, or the last 28 days of available dosing data (for subjects who discontinued treatment early). All available data points in the time interval will be used for this calculation.

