Min, Max	(xxxx.x, xxxx.x)	(xxxx.x, xxxx.x)	(xxxx.x, xxxx.x)	(xxxx.x, xxxx.x)	(xxxx.x, xxxx.x)
Week 24: raw					
n	xxx	xx	xx	xx	xx
Mean	xxxx.x	xxxx.x	xxxx.x	xxxx.x	xxxx.x
Std	xxxx.xx	xxxx.xx	xxxx.xx	xxxx.xx	xxxx.xx
Median	xxxx.x	xxxxx.x	xxxx.x	xxxx.x	xxxx.x
Min, Max	(xxxx.x, xxxx.x)	(xxxx.x, xxxx.x)	(xxxx.x, xxxx.x)	(xxxx.x, xxxx.x)	(xxxx.x, xxxx.x)

PROGRAM\OUTPUT: T\_xxxxx.SAS\T\_xxxxxx.LST

DATE (TIME) : DDMMYY (HH:MM)

Reference: Listing 16.2.6.

PROTOCOL: INCB 18424-258  
 DRUG/INDICATION: Ruxolitinib/Myelofibrosis

(Page 2 of 2)  
 VERSION: Final

Table 14.2.2.1

Summary of Spleen Volume (cm^3) by Study Week and Final Titrated Dose Group  
 (Population: ITT Subjects)

Study Week Variable	Total (N=xxx)	Ruxolitinib Final Titrated Dose (mg) Group			
		< 5 (N=xx)	>5 to 15 (N=xx)	>15 to 25 (N=xx)	>25 (N=xx)
Week 24: Chg from Baseline					
n	xxx	xx	xx	xx	xx
Mean	xxxx.x	xxxx.x	xxxx.x	xxxx.x	xxxx.x
Std	xxxx.xx	xxxx.xx	xxxx.xx	xxxx.xx	xxxx.xx
Median	xxxx.x	xxxx.x	xxxx.x	xxxx.x	xxxx.x
Min, Max	(xxxx.x, xxxx.x)	(xxxx.x, xxxx.x)	(xxxx.x, xxxx.x)	(xxxx.x, xxxx.x)	(xxxx.x, xxxx.x)
p-value from t-test	0.xxxx	0.xxxx	0.xxxx	0.xxxx	0.xxxx
p-value from WRS-test	0.xxxx	0.xxxx	0.xxxx	0.xxxx	0.xxxx
Week 24: %Chg from Baseline					
n	xxx	xx	xx	xx	xx
Mean	xxxx.x	xxxx.x	xxxx.x	xxxx.x	xxxx.x
Std	xxxx.xx	xxxx.xx	xxxx.xx	xxxx.xx	xxxx.xx
Median	xxxx.x	xxxx.x	xxxx.x	xxxx.x	xxxx.x
Min, Max	(xxxx.x, xxxx.x)	(xxxx.x, xxxx.x)	(xxxx.x, xxxx.x)	(xxxx.x, xxxx.x)	(xxxx.x, xxxx.x)
p-value from t-test	0.xxxx	0.xxxx	0.xxxx	0.xxxx	0.xxxx
p-value from WRS-test	0.xxxx	0.xxxx	0.xxxx	0.xxxx	0.xxxx

PROGRAM\OUTPUT: T\_xxxxx.SAS\T\_xxxxxx.LST

DATE (TIME) : DDMMYY (HH:MM)

Reference: Listing 16.2.6.

PROTOCOL: INCB 18424-258  
 DRUG/INDICATION: Ruxolitinib/Myelofibrosis

(Page 1 of 1)  
 VERSION: Final

Table 14.2.2.2

Summary of Proportion of Subjects with  $\geq 35\%$  Reduction from Baseline in Spleen Volume at Week 24  
 by Final Titrated Dose Group  
 (Population: ITT Subjects)

Study Week Variable	Total (N=xxx)	Ruxolitinib Final Titrated Dose (mg) Group			
		< 5 (N=xx)	>5 to 15 (N=xx)	>15 to 25 (N=xx)	>25 (N=xx)
Week 24: Reduction of $\geq 35\%$ from Baseline - n (%)					
No	xxx (xx.x)	xxx (xx.x)	xxx (xx.x)	xxx (xx.x)	xxx (xx.x)
Yes	xxx (xx.x)	xxx (xx.x)	xxx (xx.x)	xxx (xx.x)	xxx (xx.x)
95% CI for response rate [1]	(xx.x, xx.x)	(xx.x, xx.x)	(xx.x, xx.x)	(xx.x, xx.x)	(xx.x, xx.x)
Reasons for not Achieving the reduction of $\geq 35\%$ - n (%)					

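### By-dose responder tables score early dropouts as non-responders mainly in the starting-dose column, which can create a false gap between dose groups

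*SAP*

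**What the plan says.** The shell for Table 14.2.2.2 gives Yes and No counts for a spleen volume reduction of at least 35% at Week 24, in a Total column and four final-titrated-dose columns. A block that opens "Reasons for not Achieving the reduction of" 35% then lists "Discontinued prior to Week 24" and a row for missing or out-of-window data, each with n (%) in every column. Table 14.2.2.3 (at least 10% reduction) follows the same layout. Table 14.2.3.2 (at least 50% TSS improvement) and the palpation Tables 14.2.4.2 and 14.2.4.3 follow it too, but the programmer is told to leave the reasons out.

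The denominator is ITT, meaning everyone enrolled and dosed: "All efficacy analyses will be conducted using the ITT population" (SAP 5.3.2).

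A subject's column comes from SAP 5.9.3.1. This averages the total daily dose over Days 141 to 168, "or the last 28 days of available dosing data (for subjects who discontinued treatment early").

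On the schedule, "All subjects will begin dosing at 5 mg bid ruxolitinib" (SAP 4.1), and "Dose increases can occur no more frequently than every 4 weeks" (Protocol 8.6.1), starting at Week 4 in 5 mg/day steps. The SAP was written against Amendment 1 and adds: "Doses may never exceed 15 mg bid, and no dose increases may occur after Week 16". The current protocol differs on later dosing, but the starting dose and the 4-week spacing are the same in both.

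SAP 7.2 calls these summaries descriptive and states no missing-data rule.

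**The concern.** Counting dropouts as non-responders is reasonable for a single group or a randomised arm. It is not neutral across columns defined by a dose that takes time on treatment to reach. A subject has to stay on drug to enter a higher column, and leaving early is scored as failure in whatever column has been reached by then. This is a form of immortal-time bias. The non-response that comes from dropout is steered towards the starting-dose column.

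A secondary objective is an appropriate dosing strategy for patients with low platelets, and Protocol 12.2.2 commits to summaries by final titrated dose. A reader comparing '>5 to 15' with '>15 to 25' could take part of this artefact for a benefit of the higher dose.

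**Working it through.** **Plan figures.** The documents give no figure for these tables. The relevant interim figure (Protocol 4.1.5) is "8 (16.0%) discontinued prior to Week 24": 8/50 = 16.0%, which reproduces. Leaving out the 9 subjects still ongoing gives 8/41 = 19.5%. The sample-size figures concern the correlation test. They also reproduce (power 96.4%, 87.4% and 69.3% against the stated 96%, 87% and 69%) but do not enter here.

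**Step 1: which columns a dropout can reach.** Under the fastest permitted titration on nominal visit days, dose is 10 mg/day on Days 1-28, 15 on Days 29-56, 20 on Days 57-84, 25 on Days 85-112 and 30 from Day 113.
- The 28-day average first exceeds 15 on Day 57: (27 × 15 + 20)/28 = 15.18.
- It first exceeds 25 on Day 113: (27 × 25 + 30)/28 = 25.18.

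So dropouts in the first 8 weeks cannot be above 15 mg/day, and dropouts in the first 16 weeks cannot be in '>25'. An early-termination scan handled as unscheduled counts as Week 24 only within Days 141-175 (SAP 5.9.1), so it rarely rescues an early dropout.

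**Step 2: size, by algebra.** Let d be the dropout fraction, p the completer response (equal at every dose), h the share of completers above 15 mg/day, and f the share of dropouts at or below 15 mg/day.
- Rate at ≤15: p(1−d)(1−h) / [(1−d)(1−h) + d·f]
- Rate at >15: p(1−d)h / [(1−d)h + d(1−f)]

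Take d = 0.16. The interim response was 20.0%, with no denominator given. If dropouts were counted in it, the completer rate would be about 0.200/0.805 = 24.8%, so I assume p between 20% and 25%. The protocol says most subjects reached 10 mg bid or more, so I assume h between 60% and 80%. With p = 0.25 and h = 0.70, completers are 0.84 × 0.30 = 0.252 (low) and 0.84 × 0.70 = 0.588 (high). Responders are 0.063 and 0.147.

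| f | ≤15 mg/day | >15 mg/day | Gap (points) |
|---|---|---|---|
| 1.00 | 0.063/0.412 = 15.3% | 0.147/0.588 = 25.0% | 9.7 |
| 0.75 | 0.063/0.372 = 16.9% | 0.147/0.628 = 23.4% | 6.5 |
| 0.50 | 0.063/0.332 = 19.0% | 0.147/0.668 = 22.0% | 3.0 |
| 0.30 (= 1−h) | 0.063/0.300 = 21.0% | 0.147/0.700 = 21.0% | 0 |

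For f from 0.75 to 1, d from 16% to 19.5%, and the assumed ranges of p and h, the gap runs from 3.8 to 13.7 points.

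**Step 3: size, by simulation.** Four-weekly titration was simulated with dropout and response both independent of dose. Between 53% and 84% of dropouts landed at ≤15 mg/day. The false gap was 2.3 to 9.6 points, always in favour of the higher doses. Among completers it was about 0.

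**Step 4: shape.** One simulated setting had 19.5% dropout spread evenly, 25% completer response, and about 62% of completers at 20 mg/day or more:

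| Column (mg/day) | Dropouts in column | Response shown |
|---|---|---|
| up to 5 | 13.7% | 21.5% |
| >5 to 15 | 31.8% | 17.0% |
| >15 to 25 | 11.5% | 22.2% |
| >25 | 5.6% | 23.6% |

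The deficit sits in the starting-dose column and does not climb steadily from the lowest. The simulation does not include the platelet withdrawal rule at 5 mg qd (Protocol 8.7.1), which would add dropouts to the lowest dose.

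**The case against.** The strongest reply has five parts.

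- **Disclosure.** Tables 14.2.2.2 and 14.2.2.3 print the dropout and missing counts per column, so a reader can derive the evaluable rate. This stands for those two tables. It does not help with Tables 14.2.3.2, 14.2.4.2 and 14.2.4.3, where the rows are dropped, or with the by-dose responder bar plots in SAP 10.2, whose titles promise no such breakdown.
- **Weight.** A reader might infer that these tables are the main evidence on dose. No passage says so. The dose-effect question is carried by the co-primary correlations on paired observations (SAP 7.1), which this rule does not touch. By-dose percent changes with their own n are also planned. No test between columns is planned, and column intervals are wide: 8/50 has an exact 95% interval of 7% to 29%.
- **Competing selection.** Within the core phase, doses above 10 mg bid require an unfavourable PGIC score, so the highest doses are selected for poor response. That pushes the other way, and the simulation does not represent it.
- **Unsettled placement.** SAP 5.9.3.2 refers to discontinued subjects with no last titrated dose, although 5.9.3.1 gives them one. Without a dose they would have no column. The per-column dropout row implies that they have one, but the text needs reconciling.
- **Completer rates are selected too.** Subjects may leave because a dose failed or was not tolerated, and removing them hides that. The gap closes in the calculation only because response and dropout were made independent of dose. This is a good reason not to replace the ITT rates outright.

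**Conclusion.** The point holds as a limited one. The shell, the 28-day dose rule and the titration schedule together steer dropout non-response into '>5 to 15' and can produce a gap against '>15 to 25' with no dose effect. The size is roughly 2 to 10 points at 16% to 19.5% dropout, more with very brisk titration or if nearly all dropouts leave at low dose (up to 13.7 in the algebra), and zero if dropouts share the completers' dose mix. Against an interim response of 20.0%, the upper part of that range would matter. Titration speed, dropout timing, completer dose mix and completer response are assumptions that the documents do not settle.

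A reader might infer that the plan builds in a rising dose-response across all columns, or that the primary result is compromised. The documents support neither: the artefact need not be monotone, and the co-primary correlations and the Total column are unaffected. It is worth correcting because the correction is cheap.

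**What to change.** - Keep the ITT non-responder rate in the Total column of Tables 14.2.2.2, 14.2.2.3 and 14.2.3.2.
- In the by-dose part, either give dropouts their own column, or print beside the ITT rate a labelled response rate with exact 95% interval among subjects with a Week 24 value.
- Print the dropout and missing rows in Table 14.2.3.2 as well. The same treatment suits the palpation responder tables.
- Apply the same choice to the by-dose responder bar plots.
- State the missing-data rule in SAP 7.2, and reconcile 5.9.3.1 with 5.9.3.2 on whether a dropout has a final titrated dose.

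The cost is shell and programming work, with no new data. The Week 24-evaluable rates are completer rates with their own selection and must be labelled so. Titrated dose remains a non-randomised comparison under either display.
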